4.1 Inclusion Criteria

Inclusion Criteria:

- ages 12-18, male or female
- Depressed adolescent participants will have a primary diagnosis of MDD based on a clinical and structured interview with the MINI
- Depression symptoms severity of a 40 or greater based on evaluation with the Children's Depression Rating Scale Revised (CDRS-R) at screening and baseline visits. Further, the total score of the baseline CDRS-R score must not have had a 25% or greater decrease from the screening CDRS-R score
- The duration of the current episode of depression must be 4 weeks or more but 3 years or less.
- For any participant currently receiving antidepressant medication, the referring clinician must determine that insufficient benefit is being received from this treatment and it is clinically appropriate to discontinue the existing antidepressant. Participants will need to have stopped taking antidepressants at least 1 week prior (4 weeks for fluoxetine) to the baseline visit.
- Participants in psychotherapy are eligible provided that this was initiated 4 weeks prior to enrollment and that the frequency of visits will be maintained during study participation.

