Recent work in adult humans with 7 T MRS and short echo time sequences has enhanced the detection and resolution of GABA, glutamate and glutamine. Spectra will be acquired from a voxel placed in the OCC using the STEAM sequence. Voxels will be prescribed using anatomical landmarks from T1-weighted images. Spectra will be stored separately for subsequent automatic frequency and phase correction (in-house written Matlab routines) using the NAA signal at 2.01 ppm. Summed spectra will be analyzed using LCModel 6.1-4A (Stephen Provencher Inc., Oakville, ON, Canada) and simulated basis sets with a metabolite-nulled macromolecule spectrum measured in vivo. No baseline correction, zero-filling or apodization functions will be applied to the in vivo data prior to the analysis. LCModel fitting will be performed over the spectral range from 0.5 to 4.2 ppm. The quantification will be performed using the unsuppressed water signal obtained from the same voxel. Concentrations will be corrected for cerebrospinal fluid content (the tissue composition will be obtained via voxel segmentation using T1-weighted images acquired at 3 T).

The first MRS will take place following the screening visit but before the baseline/treatment visit occurs. Therefore, a 7 day window is the allowed timeframe for the first MRI and MRS scan. The second MRS will take place within 2 months of completing all rTMS phase I treatments and assessments and before beginning Phase 2 treatments. Screening will include University of Minnesota Center for Magnetic Resonance Research systematic safety assessments for safety to undergo both rTMS and ultra-high field (7 T) MRI/MRS.

Please note that travel time from Mayo Clinic Rochester to the CMRR is approximately 1 hour. Participants will be remunerated \$100.00 per scan for their time and travel expenses.

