Institutional Review Board (IRB) approval will be obtained for the consent and assent form. The investigators will describe the study in full and complete a series of written comprehension questions to verify an understanding of the discomforts and potential benefits to the study. Participants and parents will then be asked to sign the consent and assent forms prior to participation. [name] or a research team member that [name] has trained and supervises will explain the details of the study, answer any study related questions, and obtain informed assent and consent from the participants and their parents or legal guardians. [name] or a board-certified child and adolescent psychiatrist will be available 24 hours a day to address any questions participants or parents have in signing informed consent or in the course of study participation. [name] and the study team will reinforce that declining study participation does not impact accessibility to standard psychiatric treatment within the Mayo Clinic system or surrounding community. [name] will offer ongoing standard clinical care or appropriate referrals (based on patient preference) to patients who exit the study or complete all study procedures.

After providing informed consent and assent, participants will undergo an initial clinical assessment with a structured diagnostic interview (MINI), urine drug screen, safety screens, symptom rating scales, and a neurocognitive battery with the NIH tool box.⁸⁶ Participants will then undergo TMS neurophysiology testing to generate a baseline ICF (interstimulus interval of 15 milliseconds) measure for the purpose of stratification. Baseline visits study procedures can be performed on the same date at Screening visit procedures or over 2-3 separate visits based on Participant preference and comfort. Upon completion of baseline measurements and procedures, participants will be randomized to 1 Hz or 10 Hz rTMS.

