6.1 Phase I Visit 1 (Screening)

Table 2 describes all study assessments. Table 3 describes a schedule of events. The first visit is a screening visit. Informed consent and assent will be completed. A physical exam, vital signs, urine drug screen, and urine pregnancy test (if applicable) will be completed. Baseline assessments may be completed at this time as well in the interest of decreasing patient burden related to study procedures (see Table 3).

Once eligibility criteria are met and interest in the MRI/MRS is indicated, the subject will report to the University of Minnesota Center for Magnetic Resonance Imaging for the 3 and 7 Tesla MRI Scans. This procedure needs to be completed prior to the Baseline Visit.

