- A maximum of 7 days may elapse between the screening and baseline visits; a maximum of 5 days may elapse between the baseline visit and the first treatment day of Week 1. All baseline assessments must be completed before 1st TMS treatment.
- The first visit during each week of treatment should occur on a Monday, with daily treatment sessions occurring on Monday through Friday of each week.
- Participants who prematurely discontinue should complete all Week 6 procedures within 2 days after their last TMS treatment session.
- Efficacy and neuropsychological assessments to be performed after last TMS treatment session on last day of the treatment week when assessments are required. YMRS to be completed if symptom indicating mania occurs. If positive, a MINI/MINI-Kid must be repeated to determine if Participant meets full DSM-5 criteria for mania or hypomania. If positive, participant to be discontinued from the study and followed clinically.
- If Participant is female of childbearing potential, a urine pregnancy test will be performed at screening. Note that parents or guardians will not be told the results of the pregnancy test without the participant's permission. But if the participant's doctor believes that being pregnant may cause serious health problems, they may need to tell the parent/guardian the pregnancy test results.
- Adverse events occurring prior to randomization will be recorded as part of each patient's medical history. Those AEs occurring following the first TMS treatment session through 30 days after last TMS treatment session will be collected.
- In addition to the indicated day, Motor Threshold Determination (MT) may be repeated at any time during the course of the active TMS treatment sessions based on clinical assessment of the supervising physician.
Medication treatment for emergent insomnia and emergent anxiety is permitted (refer to protocol for usage allowance). Refer to Appendix A for the Concomitant Medication List.

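### The antidepressant washout is counted back from the baseline visit, but the optional baseline MRS is done up to 7 days before that visit, so a compliant participant can be scanned before the protocol's own drug-free interval has elapsed

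*Combined protocol and SAP*

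**What the plan says.** **Washout.** Section 4.1 (Inclusion Criteria) states: "Participants will need to have stopped taking antidepressants at least 1 week prior (4 weeks for fluoxetine) to the baseline visit". Section 4.2 excludes concurrent psychotropic medication but gives no number of days off drug.

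**MRS timing.** Section 3.1 (General Design) states: "The first MRS will take place following the screening visit but before the baseline/treatment visit occurs", and then "Therefore, a 7 day window is the allowed timeframe for the first MRI and MRS scan". Section 6.1 agrees: "This procedure needs to be completed prior to the Baseline Visit". The scan is offered "Once eligibility criteria are met and interest in the MRI/MRS is indicated". Table 3 marks it in the screening column.

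**Gap between visits.** A footnote to Table 3 states: "A maximum of 7 days may elapse between the screening and baseline visits".

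**ICF timing.** Section 6.2 and Table 3 place the neurophysiology measures at Visit 2 (Baseline). Section 4.3 adds flexibility: "Baseline visits study procedures can be performed on the same date at Screening visit procedures or over 2-3 separate visits". Section 6.1 does the same: "Baseline assessments may be completed at this time as well in the interest of decreasing patient burden".

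**Analysis.** For Exploratory Aim 3, section 7.2 fits separate mixed models of GABA and Gln/Glu change in the 1 Hz and the 10 Hz group, and compares depressed adolescents with healthy controls at baseline. It names no medication covariate for this aim.

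**The concern.** The washout has one anchor, the baseline visit. The baseline MRS, in those who accept it, must come before that anchor. The protocol thus sets a minimum time off antidepressants for the visit but none for the measurement.

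Two exploratory analyses are exposed:

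- **Aim 3b (change over six weeks).** Each arm is modelled separately, so randomisation does not cancel a shift that both arms share. The hypotheses run in opposite directions (GABA up with 1 Hz and down with 10 Hz, Gln/Glu the reverse). A common washout shift would tend to support one arm's hypothesis and mask the other's.
- **Aim 3a (depressed versus control).** Section 4.2.2 excludes controls with any psychiatric treatment. Some depressed participants may have stopped an antidepressant only days before the scan. A residual drug effect would then be mixed with the disease contrast.

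Section 4.1 expressly provides for participants who stop an antidepressant to enter, so the situation is foreseeable.

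**Working it through.** **Inputs**

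- W, minimum days off drug at the baseline visit: 7, or 28 for fluoxetine (section 4.1).
- g, days from the measurement to the baseline visit: more than 0 and at most 7 for the first MRS (section 3.1, section 6.1, Table 3 footnote).

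**The plan's own figure.** Section 3.1 gives a 7-day window for the first scan. It equals the maximum of 7 days from screening to baseline in the Table 3 footnote, so the figure is reproduced. The Table 3 column header (weeks -2 to -1) is looser, but its day row (-7) and the footnote both give 7, and 7 is used here.

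**Minimum days off drug at the measurement = W − g**

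| g (days before baseline visit) | Non-fluoxetine: 7 − g | Fluoxetine: 28 − g |
|---|---|---|
| 0 (at the baseline visit) | 7 | 28 |
| 1 | 6 | 27 |
| 3 | 4 | 25 |
| 6 | 1 | 22 |
| 7 (on the screening date) | 0 | 21 |

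For g from 1 to 7 the minimum is 6 down to 0 days, or 27 down to 21 for fluoxetine. A scan the day after screening, with the full 7-day gap (g = 6), gives 1 day.

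**Contrast with the second scan.** Take a participant at the 7-day minimum who starts treatment directly after baseline, completes six weeks and takes no further antidepressant. At day 40 to 42 the time since the last antidepressant dose is 7 + 40 = 47 to 7 + 42 = 49 days. The pre/post change for that participant spans a change from 0–6 days off drug to about 47 days or more.

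**Does another passage close the gap?**

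- Section 4.2 rules out a participant who is still taking a psychotropic, but adds no interval.
- Section 6.1 requires eligibility before the scan. The washout criterion, however, refers to a visit that has not yet happened, so this gate does not secure the interval at the scan.
- No passage sets a minimum time off drug at the MRS or at the ICF.

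**ICF.** By default it is taken at Visit 2, so g = 0 and the full interval applies. Only if procedures are split, with ICF before the date treated as the baseline visit, is g above 0. The protocol does not say which date that is.

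**Size of the bias.** This needs three things the documents do not give: how many participants stop an antidepressant to enter, how close to the scan they stop, and how far GABA, glutamate or glutamine differ between 0–6 days and at least 7 days off drug.

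**The case against.** The strongest reply is that 0 days is a corner case. It needs a non-fluoxetine drug, the last dose on the screening day, the full 7-day gap, and a scan that same day at a centre about an hour away. Concurrent psychotropics are excluded, and the scan follows an eligibility check. Anyone who stopped 14 days before baseline (non-fluoxetine) is unaffected, and Aim 3 is exploratory in an optional subset. All of this stands and limits the weight of the point. It does not remove the mismatch, because any scan before the baseline visit can fall short of the stated interval.

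It can also be said that the data are largely collected. Section 5.8.1 records medications taken within six months of enrolment, and the ATHF is completed. That is correct and makes the remedy cheap, but no planned Aim 3 analysis uses time since last dose.

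A reader might infer that participants land in the wrong ICF stratum and the primary analysis is compromised. The documents do not support this. ICF is assigned to Visit 2, Table 3 has no neurophysiology mark at screening, and no antidepressant effect on ICF is given. If all baseline procedures fall on the screening date, that date is arguably the baseline visit and the full washout applies. Randomisation within strata also protects the 1 Hz versus 10 Hz comparison.

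**Conclusion.** The point holds for the optional baseline MRS. A compliant participant can be scanned about 0–6 days off drug where section 4.1 requires at least 7 by the baseline visit, or 21–27 where it requires at least 28 for fluoxetine. This rests only on the dates in the protocol. Whether it biases Aims 3a and 3b in practice depends on how many participants stop shortly before the scan and on the drug effect, both unknown. For ICF the exposure is conditional on split procedures and an undefined baseline date.

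Two further inferences go too far. One is a specific inflated false-positive rate for Aim 3b: any such figure would come from assumed inputs, and the relevant quantity is the increment between 0–6 days and at least 7 days off drug, not a full drug effect in everyone recently medicated. The other is that the post-treatment scan is always free of drug: section 5.8.2 permits up to 14 doses of lorazepam or a hypnotic during Phase I, so only antidepressants can be taken as absent.

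**What to change.** 1. **Reconcile the passages.** The washout anchor in section 4.1 and the MRS timing in sections 3.1 and 6.1 should be made consistent, and the protocol should state which date counts as the baseline visit when procedures are split. How this is done clinically is for the sponsor to decide.
2. **Derive one field.** Record days since the last antidepressant or other psychotropic dose, including permitted lorazepam or hypnotics, at each MRS and at the baseline ICF.
3. **Pre-specify one sensitivity analysis.** Repeat Aims 3a and 3b without depressed participants whose first scan came before the interval stated in section 4.1 had elapsed, and report how many were excluded. This addresses the timing mismatch, not any drug effect that persists beyond the stated interval.

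**Cost.** One derived field, mostly from data already collected, one extra analysis, and somewhat lower precision in it. As an illustration only, if 5–15% of participants were excluded, standard errors would rise by a factor of 1/√0.95 = 1.03 to 1/√0.85 = 1.08. The main Aim 3 analysis keeps everyone.

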4.1.1 Inclusion Criteria Healthy Controls

- ages 12-18, male or female

4.2 Exclusion Criteria

Exclusion Criteria:

- The following psychiatric comorbidities are exclusionary: psychotic disorders, bipolar disorders, anorexia nervosa, bulimia nervosa, and substance use disorders within the past year (with the exception of caffeine and tobacco)
- A positive urine drug screen at baseline
- Seizure history
- Family history of epilepsy in a first degree relative

- Head trauma with loss of consciousness for greater than 5 minutes
- Any true positive findings on the rTMS safety screening form.
- Contraindications to MRI/MRS (CMRR Subject Safety Screening Form)
- Any concurrent psychotropic medications (for potential participants receiving antidepressants or psychotropic medications, the referring clinician must determine that insufficient benefit is being received from the treatment and if clinically appropriate, discontinue existing antidepressants and other psychotropic medications).
- Prohibited concomitant medications (See Appendix A)
- Pregnancy or suspected pregnancy in female Participants (assessed with urine pregnancy test)
- Conductive, ferromagnetic, or other magnetic-sensitive metals implanted in the subject's head within 30 cm of the treatment coil excluding the mouth that cannot safely be removed. Examples include cochlear implants, implanted electrodes/stimulators, aneurysm clips or coils, stents, bullet fragments, jewelry and hair barrettes.
- Prior brain surgery
- Risk for increased intracranial pressure such as a brain tumor
- Any unstable medical condition
- History of treatment with ECT or TMS Therapy for any disorder
- Use of any investigational drug within 4 weeks of the baseline visit
- Initiation of a new psychotherapeutic treatment within the past 4 weeks
- Suicide attempt within the previous 6 months that required medical treatment or ≥ 2 attempts in the past 12 months, or has a clear cut plan for suicide and states that he/she cannot guarantee that he/she will inform a family member or call his/her psychiatrist or the investigator if the impulse to implement the plan becomes substantial during the study; or, in the investigator's opinion, is likely to attempt suicide within the next 6 months.

4.2.2 Exclusion Criteria Healthy Controls

- History of depression or any psychiatric treatment
- Subjects found to be pregnant at time of screening will be ineligible
- Positive urine drug screening
- Contraindications to MRI/MRS (CMRR Subject Safety Screening Form)

4.3 Participant Recruitment, Enrollment and Screening

Participants will be recruited from the general community and referrals from local providers. Currently [name] directs a research program and outpatient clinic for adolescent mood disorders. Our group historically has been successful in the recruitment of similar samples.

Additional resources will be utilized for recruitment of potential participants including:

- from within the clinical and referral practices of the clinical study site
- referrals from other care providers within the treatment communities
- radio advertisements
- invitation letters sent to parents of potentially eligible participants
- print advertisements, including but not limited to brochures, flyers, and listings in research classifieds
- trial listing with ClinicalTrials.gov
- trial listing on university and clinical study site website

- social media

All advertising materials will be reviewed and approved by the Mayo Clinic IRB prior to use.

Potentially interested adolescents and their families may be provided with printed participant educational materials to aid them in making an informed decision regarding their willingness to participate in this study. In addition, parents of potentially eligible patients identified via i2b2 search will be contacted via IRB-approved email and follow-up telephone calls if necessary.

Institutional Review Board (IRB) approval will be obtained for the consent and assent form. The investigators will describe the study in full and complete a series of written comprehension questions to verify an understanding of the discomforts and potential benefits to the study. Participants and parents will then be asked to sign the consent and assent forms prior to participation. [name] or a research team member that [name] has trained and supervises will explain the details of the study, answer any study related questions, and obtain informed assent and consent from the participants and their parents or legal guardians. [name] or a board-certified child and adolescent psychiatrist will be available 24 hours a day to address any questions participants or parents have in signing informed consent or in the course of study participation. [name] and the study team will reinforce that declining study participation does not impact accessibility to standard psychiatric treatment within the Mayo Clinic system or surrounding community. [name] will offer ongoing standard clinical care or appropriate referrals (based on patient preference) to patients who exit the study or complete all study procedures.

After providing informed consent and assent, participants will undergo an initial clinical assessment with a structured diagnostic interview (MINI), urine drug screen, safety screens, symptom rating scales, and a neurocognitive battery with the NIH tool box.⁸⁶ Participants will then undergo TMS neurophysiology testing to generate a baseline ICF (interstimulus interval of 15 milliseconds) measure for the purpose of stratification. Baseline visits study procedures can be performed on the same date at Screening visit procedures or over 2-3 separate visits based on Participant preference and comfort. Upon completion of baseline measurements and procedures, participants will be randomized to 1 Hz or 10 Hz rTMS.

Preventing participant attrition during investigational, therapeutic TMS: Treatment sessions are delivered 5 days per week consistent with prior systematic research.^{33,47,83, 38} We will offer treatment sessions on the weekend (for a total of 5 weekly sessions) when necessary to accommodate the participant scheduling constraints over a period of 6 weeks. Hence participants will be given 42 opportunities to complete 30 sessions of rTMS. During the first week of rTMS treatment intensity may be adjusted for participant comfort to a minimum of 80% motor threshold and titrated by 10% daily to 120% of resting motor threshold. We have found that these scheduling and titration procedures are highly effective for retaining adolescent participants for investigational therapeutic rTMS

It is anticipated that 150 participants will be screened to enroll 120 participants for Phase I. A maximum of 50 participants will be enrolled in Phase II. Prior clinical experience and research with 10 Hz and 1 Hz rTMS suggests that approximately 50% of Phase I participants (N=60) will

not respond to treatment and thus will be eligible for Phase II. Please note that Phase II is an exploratory study and also intended to provide an additional resource for participants who do not respond to standard rTMS approaches. Based on prior work it is unlikely that no more than 50 participants will be eligible and interested in enrollment in Phase II.

4.4 Early Withdrawal of Participants

4.4.1 Participant Withdrawal, Data Collection, and Follow-Up

Participants may withdraw voluntarily from the study at any time. Participants will be withdrawn from the study by the PI/Sponsor if a participant:

- experiences a seizure,
- experiences a DSM-5-confirmed treatment-induced mania,
- is non-compliant with study procedures; or
- endorsed illicit drug use or has a positive urine drug screen during the study

The PI may also withdraw a participant if he/she believes that for safety reasons it is in the best interest of the participant to be withdrawn.

Discontinuation information [e.g., date and the reason(s) for discontinuation] will be recorded in the Participant's CRF (Case Report Form). Participants who discontinue prematurely should complete the Week 6 assessment procedures within 2 days following their last TMS treatment session. See the Schedule of Events for the specific procedures to be performed at this discontinuation visit.

Participants withdrawn from the study due to an AE will be followed up for 30 days or until resolution. Participants withdrawn from the study will not be replaced, regardless of the reason for withdrawal. An effort will be made to determine why a participant does not return for the required visits or is dropped from the study. This information will subsequently be recorded on the participant's CRF. Participants will be encouraged to remain compliant with all expected study visits. Non-adherence to expected study visits will be documented and may result in removal from the study. This will be clearly discussed during the consent/assent process and reinforced throughout the study through regular screening for issues with compliance.

[name] will assist with clinical referral for all participants who voluntarily withdraw from the study or are withdrawn by the research team and PI. Specifically, [name] will offer ongoing clinical care or community referrals based on the preference of the participant.

5 Study Device

